11.7 Confidentiality of study documents and patient records

The investigator must ensure anonymity of the patients; patients must not be identified by names in any documents submitted to Recordati. Signed informed consent forms and patient enrollment log must be kept strictly confidential to enable patient identification at the site.

11.8 Audits and inspections

Source data/documents must be available to inspections by Recordati or designee or Health Authorities.

Recordati will delegate some trial-related activities to the CRO IQVIA. IQVIA has in place its own Quality Management System to ensure compliance with written Standard Operating Procedures as well as applicable global/local GCP regulations and ICH Guidelines.

Recordati will maintain the oversight of any trial-related duties, functions and delegated activities that will be subcontracted to IQVIA.

11.9 Financial disclosures

Financial disclosures should be provided by study personnel who are directly involved in the treatment or evaluation of patients at the site, prior to study start.

12 Protocol adherence

Investigators ascertain they will apply due diligence to avoid protocol deviations. Under no circumstances should the investigator contact Recordati or its agents, if any, monitoring the study to request approval of a protocol deviation, as no authorized deviations are permitted. If the investigator feels a protocol deviation would improve the conduct of the study this must be considered a protocol amendment, and unless such an amendment is agreed upon by Recordati and approved by the IRB/IEC/REB it cannot be implemented. All significant protocol deviations will be recorded and reported in the CSR.

14.1 Appendix 1: Medications known to be associated with QT interval prolongation

The list of drugs is generally recognized to have a possible association with QT prolongation can be found at [//crediblemeds.org](http://crediblemeds.org). This list is not considered to be all inclusive and any questions regarding the QT prolongation potential should be discussed with the Recordati Medical Monitor.

14.2 Appendix 2: Recommended hepatic safety management guidance

Patients with transaminase increase combined with TBIL increase may be indicative of potential DILI, and should be considered as clinically important events.

If any of the criteria below are observed at any routine examinations (standard of care),

- ALT or AST $> 3 \times$ ULN and Total Bilirubin $\geq 2 \times$ ULN.
- ALT or AST $> 5 \times$ ULN and $\leq 8 \times$ ULN.
- ALT or AST $> 8 \times$ ULN, patient should be discontinued.

The following should be performed immediately within **72 hours** of awareness of the abnormality (for further details refer to [Figure 14-1](#)):

- Perform liver-directed medical history and physical examination (i.e. assess occupational hazards, concomitant medications including OTC meds, inter-current illness, etc).
- Liver chemistry tests: ALT, AST, total bilirubin, (fractionate to direct/indirect bilirubin if total bilirubin is $> 2.0 \times$ ULN), Alb, PT (INR), ALP, and GGT.
- Perform hepatitis screen: anti-HAV, IgM (to confirm acute Hepatitis A), HbsAg, Anti-HBc, anti-HCV (if positive, PCR viral load should be assessed), Anti-HEV, ANA antibodies, anti-smooth muscle anti-bodies, CMV and EBV.
- Perform abdominal ultrasound (liver and biliary tree).

[figure not shown]
Liver chemistry tests (LFTs) should be monitored every **3-4 days** until resolution or return to baseline status.

Patients or subjects may need to be discontinued if the abnormal liver function criteria are met upon LFT retesting. Progress reports of the event should be maintained until resolution or stabilization (i.e. no further elevation after 2 consecutive assessments).

For ALT or AST $> 5 \times$ ULN and $\leq 8 \times$ ULN, the following must occur (in addition to the safety follow up procedures noted above).

- Study medication should be temporarily interrupted and liver chemistry tests monitored every **3-4 days** until resolution or return to baseline.
- If resolution (ALT and AST ≤ 5 ULN) or return to baseline does not occur after 2 weeks, the patient should be discontinued.
- If ALT or AST return to less than 5 x ULN study drug can be resumed and patient can continue study per protocol.
- If ALT or AST rises above 5 x ULN any time after study drug is resumed, then study drug should be discontinued immediately.

If any of these criteria are met and deemed an adverse event by the investigator, the event must be recorded on the Adverse Event (e) CRF page; if the event is deemed serious by the investigator, then proceed with completing the SAE form. In addition, any significant findings from the physical examination should be recorded on the Adverse Event (e) CRF page.

[figure not shown]
Figure 14-1 Recommended LFT management guidance

14.3 Appendix 3: Recommended guidance for follow up in case of QT-related findings during routine ECG

If at any routine ECG a QTcF > 500 msec is observed, triplicate ECGs, each 2-3 minutes apart, need to be collected approximately 1 hour after the initial ECG. The mean QTcF from the triplicate ECGs will be determined and if the mean QTcF > 500 msec, study treatment should be interrupted until a cardiologist has re-evaluated the ECG. Patient reassessment should be performed as early as possible but within 7 days of the initial abnormal ECG by a cardiologist for cardiovascular risk factors and a decision regarding study continuation.

If mean QTcF > 480 msec / ≤ 500 msec is observed, the repeat ECG assessment must be performed as soon as practical but within 7 days of the initial abnormal ECG. In addition, the following steps need to be taken (for more details refer to [Figure 14-2](#) below):

- If a QTcF > 480 msec / ≤ 500 msec is confirmed and QTcF change from pretreatment exceeds 60 msec, cardiology consultation must be sought as soon as practical (within 7 days) for ECG re-evaluation and clinical assessment for cardiovascular risk factors and a decision regarding study continuation.
- If a QTcF > 480 msec / ≤ 500 msec is confirmed and QTcF change from pretreatment < 60 ms, more frequent ECG follow-up is advised.

Figure 14-2 Recommended guidance for ECG follow up

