7.1.5.1 Criteria for premature patient withdrawal

Patients may voluntarily withdraw from the study or be dropped from it at the discretion of the investigator at any time. Patients may be withdrawn from the study if any of the following occur:

- Death.
- Lost to follow-up.
- Staying in the study would be harmful.
- Patient/guardian decision.
- Physician decision.
- Non-compliance to protocol requirements.
- Protocol deviation.
- Pregnancy.
- Study terminated by sponsor.
- Study treatment has become available through country-specific programmes outside of this clinical trial (applicable to Brazil, France, Germany, India, Italy, Malaysia, Mexico, Peru and Thailand).

Study treatment has become commercially available and reimbursed (when current treatment becomes commercially available and reimbursed in that indication, the patient will have to be withdrawn from the study and will have completed the study as per protocol).

In addition to the general withdrawal criteria, the following criteria may also require study treatment discontinuation:

If any of the criteria below are met during routine examinations that are part of standard of care, study medication should be discontinued immediately. Re-challenge of study medication is prohibited once discontinuation criteria are met.

Hepatic-related discontinuation criteria

- Jaundice or other signs of clinically significant liver dysfunction
- ALT or AST $> 3 \times$ ULN and Total Bilirubin $\geq 2 \times$ ULN and ALP $< 2 \times$ ULN
- ALT or AST $> 5 \times$ ULN and $\leq 8 \times$ ULN persistent for more than 2 weeks
- ALT or AST $> 8 \times$ ULN

QT related discontinuation criteria

- Confirmed QTcF >500 ms and discontinuation recommended by a cardiologist
- QTcF > 480 msec, if the investigator determines it is no longer safe for the patient to continue in the study, based on ECGs, cardiac examination and recommendation from a cardiologist.
- Clinically significant arrhythmias including:
 1. Any ventricular or supra-ventricular tachyarrhythmia associated with symptoms of hemodynamic compromise.
 2. Sustained ventricular tachycardia (>30 s) irrespective of symptoms.
 3. Recurrent non-sustained VT (≥ 3 beats) during any 24-hour monitoring period.
 4. Clinically significant brady-arrhythmia or third degree AV block.
 5. Need to use a drug with known risk of TdP.

Hyperglycemia related discontinuation criteria

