- Uncontrolled diabetes mellitus (DM), consistently high glucose values FPG ≥ 240 mg/dL (13.3 mmol/L) or HbA1c value ≥ 10 % despite appropriate management of diabetes including diet and/or exercise with or without optimal anti-diabetic therapy

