- If FPG > 160 mg/dL or HbA1c >7.5%, despite optimal anti-diabetic therapy, referral to a diabetologist is recommended.
- If grade 3 hyperglycemia (FPG >250 mg/dL; >13.9 mmol/L) at any point in the study, despite appropriate anti-diabetic medication, pasireotide dose should be reduced
- If consistently high glucose values [FPG \geq 240 mg/dL (13.3 mmol/L) or HbA1c \geq 10 %] despite appropriate management of diabetes including diet and/or exercise with or without

optimal anti-diabetic therapy and study drug dose reduction, patient must be discontinued from study treatment as outlined in [Section 7.1.5.1](#). After the last study dose was received, patients have to monitor their fasting blood glucose for 1 month

Figure 14-3 Recommended guidance for fasting self-monitoring blood glucose management

14.5 Appendix 5: Dose modification information for acromegaly or carcinoid patients receiving pasireotide LAR (from protocol CSOM230C2110, CSOM230C2305, CSOM230C2402 and CSOM230C2413)

At any time during the roll-over, the pasireotide LAR dose may be increased up to a maximum dose of 60 mg per injection if biochemical control is not achieved, i.e. when their GH level \geq 2.5 μ g/L and/or IGF-1 > ULN (age and sex related). Also the pasireotide LAR dose may be reduced if a patient is experiencing a drug related toxicity. The dose should be adjusted in 20 mg steps, e.g. the pasireotide LAR dose can be adjusted from 60 mg to 40 mg or from 40 mg to 20 mg. The decision to change the dose is to be made by the investigator or designee, and the dose change must be recorded in the Dosage Administration Record CRF. Patients should return to the previous dose once the tolerability issue resolves.

Study C2413 specific: The minimum dose to be administered is 10 mg for patients with IGF-1 levels falling below the lower limit of normal and have controlled mean GH levels. The IGF-1 values are required to be confirmed to be below LLN on two consecutive assessments. If biochemical control is maintained, the patient can continue on the lower dose for the remainder of the trial. If biochemical control is lost, the dose should be increased. The 10 mg dose should be obtained from the 20 mg vial.

Table 14-1 Dose modification for AEs, excluding LFT increase, QT prolongation and hyperglycemia

Adverse event	Action
CTCAE grade \leq 2	No drug adjustments

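### Protocol 7.1.5.1 prohibits re-challenge after a combined ALT/AST and bilirubin rise with ALP below 2×ULN, but the Appendix 2 text lets drug be resumed in part of that group

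*Protocol*

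**What the plan says.** **Protocol 7.1.5.1, hepatic criteria.** Four are listed: jaundice or other clinically significant liver dysfunction; ALT or AST above 3×ULN with total bilirubin at least 2×ULN and ALP below 2×ULN; ALT or AST above 5 and up to 8×ULN lasting more than 2 weeks; and ALT or AST above 8×ULN. The combined criterion has no duration condition. The lead-in is soft: it says these criteria might call for stopping treatment. The operative sentence is firmer: "study medication should be discontinued immediately. Re-challenge of study medication is prohibited once discontinuation criteria are met".

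**Protocol Appendix 2.** It opens with "Patients with transaminase increase combined with TBIL increase may be indicative of potential DILI". Three findings then trigger a work-up within 72 hours: the combined rise (with no ALP term), ALT or AST above 5 and up to 8×ULN, and ALT or AST above 8×ULN, where the patient is also to be discontinued. On stopping more generally it says "Patients or subjects may need to be discontinued if the abnormal liver function criteria are met upon LFT retesting". For the band above 5 and up to 8×ULN it introduces further steps as mandatory: "Study medication should be temporarily interrupted and liver chemistry tests monitored every" 3 to 4 days; discontinue if there is no resolution after 2 weeks; otherwise "If ALT or AST return to less than 5 x ULN study drug can be resumed and patient can continue study per protocol". It adds a later stop: "If ALT or AST rises above 5 x ULN any time after study drug is resumed, then study drug should be discontinued immediately".

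**Pointers.** Sections 2.1, 4.1 and 6.1.7 refer to Section 7.1.5 for the discontinuation criteria. Section 7.2.2.1 sends sites to Appendix 2 for any hepatic finding, and Section 6.2 sends them to Appendices 2 to 12 for dose modification.

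**SAP 8.1.** Deviation D01 covers patients who met hepatic discontinuation criteria and were not withdrawn.

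**The concern.** The Appendix 2 branch is defined by ALT or AST alone, and so is its condition for resuming. Nothing in it asks whether bilirubin was raised, whether it has recovered, or what ALP was. As written, it covers a patient for whom 7.1.5.1 rules out re-challenge.

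The overlap is small, but it concerns re-exposure after a pattern that Appendix 2 itself links to possible drug-induced liver injury. A site that follows the appendix it was sent to could restart drug against 7.1.5.1. SAP 6.1 tabulates patients who developed withdrawal criteria but were not withdrawn, so the same patient could then appear in the study report as a D01 deviation.

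**Working it through.** The plan states no figure here, so the check applies both rule sets to the same cases.

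**Inputs.** The thresholds above, from Protocol 7.1.5.1 and the Appendix 2 text.

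**Grid.** 3 ALT/AST bands × 2 bilirubin states (at least 2×ULN, or not) × 2 ALP states (below 2×ULN, or not) = 12 cells. Jaundice and other clinical signs are left out. The combined pattern below means bilirubin at least 2×ULN with ALP below 2×ULN.

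| ALT/AST (×ULN) | Cells | 7.1.5.1 | Appendix 2 text | Can both be followed? |
|---|---|---|---|---|
| >3 to 5, combined pattern | 1 | Immediate stop, no re-challenge | Work-up; stopping possible on retest | Yes |
| >3 to 5, other | 3 | No stop | Work-up if bilirubin is at least 2×ULN | Yes |
| >5 to 8, combined pattern | 1 | Immediate stop, no re-challenge | Interrupt; resumption allowed below 5×ULN | **No** |
| >5 to 8, other | 3 | Stop only if it lasts beyond 2 weeks | Interrupt; resumption allowed below 5×ULN; stop if unresolved after 2 weeks | Yes |
| >8, any | 4 | Immediate stop | Discontinue | Yes |

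Cells: 1 + 3 + 1 + 3 + 4 = 12. Section 7.1.5.1 calls for an immediate stop in 1 + 1 + 4 = 6. Appendix 2 also stops in the 4 cells above 8×ULN, which leaves 6 − 4 = 2 to examine.

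- **Above 3 and up to 5×ULN.** Appendix 2 never says to continue drug. A site can stop under 7.1.5.1 and still do the work-up, as Appendix 2 itself combines the two above 8×ULN. The wording differs, but the actions are compatible.
- **Above 5 and up to 8×ULN.** One text prohibits re-challenge and the other permits resumption. This is the one firm conflict: 1 of 12.

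**Worked case.** ALT 6×ULN, bilirubin 2.5×ULN, ALP 1×ULN. Since 6 > 3, 2.5 ≥ 2 and 1 < 2, the combined criterion is met. Since 5 < 6 ≤ 8, the Appendix 2 branch also applies. If ALT falls below 5×ULN within 2 weeks, Appendix 2 allows drug again and 7.1.5.1 does not.

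**Adding duration.** Splitting each cell at 2 weeks gives 12 × 2 = 24 combinations. A mechanical comparison flags 3: the combined pattern at >3 to 5×ULN for either duration, and at >5 to 8×ULN for up to 2 weeks. The first two are the compatible case above. The firm conflict is the third; beyond 2 weeks both texts stop.

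**Glucose wording (minor).** The 7.1.5.1 stop applies "despite appropriate management of diabetes including diet and/or exercise with or without optimal anti-diabetic therapy". Appendix 4 repeats the same limits and cites 7.1.5.1, but reads "optimal anti-diabetic therapy and study drug dose reduction, patient must be discontinued from study treatment". Appendix 4 triggers dose reduction at FPG above 250 mg/dL, while the stop begins at 240 mg/dL. A consistent FPG of 240 to 250 mg/dL can therefore meet the stop without having reached that trigger, so the added words matter if they are a condition.

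**The case against.** The strongest reply is that the documents already favour 7.1.5.1. Three sections send the reader to Section 7.1.5 for discontinuation, Appendix 2 is titled as recommended guidance, and the protocol summary treats the appendices as additional guidance. The resume branch repeats only the isolated transaminase finding and permits rather than requires resumption; its closing reference to the protocol may point back to 7.1.5.1. Figure 14-1, cited for further detail, may separate the two cases. The D01 wording also closely matches the 7.1.5.1 heading.

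Much of this stands, and it makes the intended reading easier to guess. It does not settle the text. No section ranks the two places. Section 7.2.2.1 sends every hepatic finding to Appendix 2, the branch presents its steps as mandatory, and Appendices 5, 6, 7, 8, 9 and 11 treat Appendices 2 to 4 as the instructions for LFT increases. If D01 means the 7.1.5.1 criteria, a patient resumed under Appendix 2 is the one it would capture.

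A reader might infer more than the documents support:

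- **A conflict wherever bilirubin is raised.** In the band above 3 and up to 5×ULN both texts can be followed. Part of the difference may be deliberate, since the Appendix 2 trigger is broader and its work-up measures ALP.
- **A resume rule that is wrong in general.** For isolated rises above 5 and up to 8×ULN that settle within 2 weeks, 7.1.5.1 sets no stop and the texts agree.
- **A contradiction in the re-rise stop.** It is an additional stop in Appendix 2.
- **A contradictory glucose stop.** If the phrase allowing for presence or absence of therapy also covers dose reduction, the two sentences agree.

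**Conclusion.** The point holds for one overlap: ALT or AST above 5 and up to 8×ULN, bilirubin at least 2×ULN and ALP below 2×ULN, with ALT or AST falling below 5×ULN within 2 weeks. There the two texts give incompatible instructions on re-exposure. The count of 1 in 12 measures how the rules overlap and says nothing about frequency; the documents give no number of affected patients and do not show that any patient was re-exposed or misclassified.

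The conclusion rests on the written text. If Figure 14-1 excludes the combined pattern from the resume branch, what remains is a mismatch between figure and text that still needs aligning. The soft lead-in to 7.1.5.1 leaves some room on whether stopping is automatic, but not on re-challenge once a criterion is met. No endpoint, analysis set or hypothesis test is affected. The point is worth correcting because it bears on patient safety.

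**What to change.** The sponsor's clinical team should reconcile Protocol 7.1.5.1 with Appendix 2 and Figure 14-1. The text should say whether the interrupt-and-resume branch applies when the combined 7.1.5.1 criterion is also met, and which text prevails for discontinuation. Which clinical rule is right is for that team.

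Smaller items for the same amendment:

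- say whether dose reduction in Appendix 4 is a condition of the 7.1.5.1 glucose stop;
- say whether the Appendix 2 re-rise stop belongs in 7.1.5.1;
- correct the hyperglycemia pointer in Table 14-12, which names Appendix 14.2 (the hepatic appendix). That table concerns SOM230D2101, which is not among the parent studies in SAP Tables 2-1 and 2-2.

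Optionally, SAP 8.1 can name the governing section for D01 to D03 before database lock.

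Cost: under Protocol 12.1 the amendment needs IRB/IEC/REB approval and, where required, Health Authority approval; a site letter should go with it. No new assessments, data or patients are needed.

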10.4.2 Statistical hypothesis, model, and method of analysis

No hypothesis will be tested.

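### Appendix 2 requires both liver enzymes for resolution but only one for restarting drug, so a patient with one enzyme recovered can be unresolved and yet eligible to restart

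*Protocol*

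**What the plan says.** Protocol Section 14.2 (Appendix 2) has a block for ALT or AST above 5 and up to 8 x ULN. It opens in mandatory terms: "the following must occur (in addition to the safety follow up procedures noted above". Four bullets follow.

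- Interruption: "Study medication should be temporarily interrupted and liver chemistry tests monitored every" 3 to 4 days, until resolution or return to baseline.
- Resolution and its deadline: "If resolution (ALT and AST ≤ 5 ULN) or return to baseline does not occur after 2 weeks, the patient should be discontinued".
- Restart: "If ALT or AST return to less than 5 x ULN study drug can be resumed and patient can continue study per protocol".
- After restart: "If ALT or AST rises above 5 x ULN any time after study drug is resumed, then study drug should be discontinued immediately".

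Section 7.1.5.1 separately lists, as a hepatic discontinuation criterion, ALT or AST in the same range when "persistent for more than 2 weeks". It bars rechallenge once a discontinuation criterion has been met. The ALT/AST row for this range in Table 14-12 (Section 14.10.2, for patients from SOM230D2101) repeats the restart sentence of Appendix 2.

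**The concern.** The resolution bullet joins the two enzymes with *and* and allows equality at 5 x ULN. The restart bullet joins them with *or* and requires a value strictly below 5 x ULN. The bullets are adjacent and govern the same event, so they should open and close on the same condition, and they do not.

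The rule decides whether a patient with a marked transaminase rise is held, dosed again or stopped. Two sites that both follow the text could manage the same patient differently. The reach is broad. Section 7.2.2.1 sends every hepatic finding to Appendix 2, Section 6.2 cites it among the dose-modification guidelines, and Appendices 5 to 9 and 11 defer to it for liver-test increases. Section 2.6 names transaminase elevation as an expected effect of pasireotide, and SAP Attachment 8.2 has a liver-safety category of special interest.

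**Working it through.** No figure in the plan needs reproducing. There is no sample-size calculation, and Section 10.4.2 states "No hypothesis will be tested". The check is a logical one.

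**Rules as written** (a and b are ALT and AST in multiples of ULN; all from Appendix 2):

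- Interrupt: 5 < a ≤ 8 or 5 < b ≤ 8.
- Resolved: a ≤ 5 and b ≤ 5. Return to baseline is an alternative; the cases below assume that any value above 5 is also above the patient's baseline.
- Restart, literal: a < 5 or b < 5. The verb is *return*, so the enzyme now below 5 is taken to have been above it earlier. Every case below therefore starts with both enzymes above 5.

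**Results:**

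| Current values | In interruption range | Resolved | Restart bullet met (*or*) | If restart were read with *and* |
|---|---|---|---|---|
| 7 and 6 | yes | no | no | no |
| 7 and 4 | yes | no | **yes** | no |
| 8 and 4.9 | yes | no | **yes** | no |
| 5 and 5 | no | yes | **no** | no |
| 5 and 4 | no | yes | yes | no |
| 4 and 4 | no | yes | yes | yes |

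Two separate mismatches appear.

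1. *And/or.* At 7 and 4, or 8 and 4.9, the patient is unresolved and still in the range that calls for interruption, yet meets the restart condition.
2. *Inequality.* At 5 and 5 the patient is resolved but does not meet the restart condition. The last column shows that changing *or* to *and* alone would leave this mismatch and would add the 5-and-4 case to it. Both elements need aligning.

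**Time window.** Suppose both enzymes are at 7 on day 0, and on day 7 one is at 4 and the other still at 7 (illustrative days). From day 7 to day 14 the restart bullet permits dosing while the interruption and resolution bullets do not treat the event as closed. After two weeks, the resolution bullet and Section 7.1.5.1 both point to discontinuation. With tests every 3 to 4 days, a 14-day window holds three or four repeat tests (days 4, 8, 12 or days 3, 6, 9, 12) at which the bullets could disagree.

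**Interaction with Section 7.1.5.1.** If drug is restarted on day 7 and the second enzyme stays at 7 past two weeks, the patient reaches a hepatic discontinuation criterion while on drug. That criterion makes no exception for a patient already restarted.

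**Table 14-12.** Its row carries the *or* restart wording and a 14-day limit but has no definition of resolution. The row above it runs up to and including 5.0 x ULN, so the same question at exactly 5 arises there.

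**The case against.** The best defence is that the block read as a whole limits the damage. The interruption bullet already runs until resolution, resolution is defined on both enzymes, and the restart bullet only permits. A careful investigator would probably read the three together. Section 7.1.5.1 then stops anyone whose elevation persists, so the ambiguity is largely confined to two weeks. That stands and sets the size of the point. It does not remove the point, because no legible text says that the resolution definition controls restart.

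The appendix is titled as recommended guidance, but this block is worded as mandatory. Appendix 2 also refers the reader to Figure 14-1 for further detail. The figure is not shown, and it may be clearer than the bullets. Even so, the bullets would still disagree with each other.

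A reader might infer four stronger things that the documents do not support.

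- *That a patient with only one enzyme ever above 5 x ULN qualifies for restart on the very sample that triggers interruption.* The bullet speaks of a return below 5, and an enzyme that was never above 5 has nothing to return from.
- *That the last bullet catches the 7-and-4 patient as soon as drug is restarted.* It refers to a value that rises above 5 after restart, and an enzyme that stayed at 7 throughout does not clearly meet it.
- *That a restarted LAR dose is irreversible for a fixed 28 days.* In the protocol, 28 days is the dosing interval; no such statement about reversibility is made.
- *That SAP derivations must be reprogrammed.* SAP Section 7.3 derives interruption from a zero dose followed by a non-zero dose. Deviation D01 in Attachment 8.1 refers to the hepatic discontinuation criteria, which are in Section 7.1.5.1 and contain no restart rule. The laboratory paragraph of SAP Section 4.1 covers pregnancy tests only.

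Table 14-12 applies to SOM230D2101, which is not in the SAP's tables of parent studies, so the practical reach of that row is uncertain.

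**Conclusion.** The inconsistency is real and is in the current text. For the range above 5 and up to 8 x ULN, resolution and restart differ in both the and/or logic and the inequality at 5 x ULN. The clear conflict is a patient with both enzymes initially above 5, one of which has fallen below 5 while the other stays in the interruption range. There is a smaller mismatch at exactly 5 x ULN for both. It matters mainly within the two weeks before discontinuation applies.

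No frequency can be given. The documents contain no distribution of ALT and AST, no correlation between them and no recovery times, so a claim that most patients entering this rule are affected would be unsupported. The case for correction rests on the rule governing re-dosing after a marked enzyme rise, not on a count. The conclusion assumes the literal wording, a patient baseline below the raised value, and nothing in the unseen Figure 14-1 that settles which bullet governs. Which condition is clinically right is not judged here.

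**What to change.** The sponsor should reconcile the resolution and restart bullets of Appendix 2, the matching ALT/AST row of Table 14-12, and Figure 14-1. Resolution and restart should use one identical condition: the same and/or logic and the same inequality at 5 x ULN. The result should be checked against the discontinuation criterion in Section 7.1.5.1. The sponsor's clinical team should decide which logic applies.

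The cost is a short wording correction with no new data, visits or procedures and no change to the SAP derivations. Section 12.1 requires a written amendment for any protocol change, with the usual approvals, so the administrative step is the main expense.
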